6.3.4.2. Rater qualifications and blinding

Raters will be selected based on experience appropriate for the measures and will be trained so that variability in ratings is minimized. Two separate types of trained and qualified raters will administer the cognitive/functional and functional/global scales unless a single rater is approved by the sponsor. A psychometric rater will administer measures such as the MMSE, RBANS, ADAS-Cog₁₃, NPI, EQ-5D-5L, and RUD-Lite (see Table 4). A separate, global rater will administer the FAQ, the ADCS-ADL, and the CDR. If possible, the CDR should be administered by the same rater for a given patient. It is preferred that the same rater who administers the screening tests also performs all post-screening administrations of those tests for a given patient.

Every effort should be made to prevent the CDR rater from becoming aware of any AEs the patient may experience during the study. CDR raters should, as much as possible, not have access to this information and should instruct patients and their study partners not to discuss AEs during the CDR interview. The rater should sign a statement to this effect on the CDR worksheet. Site personnel who are involved in reviewing medical data or who may have access to AE information must refrain from discussing this information with the CDR rater.

^a The CDR must always be administered to the study partner first and then to the patient. It is recommended that both sections be administered on the same day.

6.4. Safety

The Principal Investigator is responsible for ensuring that all staff involved in the study are familiar with the content of this section.

6.4.1. Definition of adverse events

An AE is the development of an undesirable medical condition or the deterioration of a pre-existing medical condition following or during exposure to a pharmaceutical product, whether or not considered causally related to the product. An undesirable medical condition can be symptoms (eg, nausea, chest pain), signs (eg, tachycardia, enlarged liver) or the abnormal results of an investigation if symptomatic or clinically significant (Section 6.4.3.6 for abnormal results; eg, laboratory findings, ECG). In clinical studies, an AE can include an undesirable medical condition occurring at any time, including run-in or washout periods, even if no study treatment has been administered.

The term AE is used to include both serious and non-serious AEs.

6.4.2. Definitions of serious adverse event

A serious AE is an AE occurring during any study phase (ie, screening, double-blind treatment, and follow-up), that fulfills 1 or more of the following criteria:

- Results in death
- Is immediately life-threatening
- Requires in-patient hospitalization or prolongation of existing hospitalization
- Results in persistent or significant disability/incapacity or substantial disruption of the ability to conduct normal life functions
- Is a congenital abnormality or birth defect
- Is an important medical event that may jeopardize the patient or may require medical intervention to prevent one of the outcomes listed above.

For further guidance on the definition of an SAE, see Appendix B to the Clinical Study Protocol.

Note: Cases where a patient shows an AST or ALT $\ge 3x$ ULN and total bilirubin $\ge 2x$ ULN may need to be reported as SAEs. Refer to Appendix D "Actions required in cases of combined increase of aminotransferase and total bilirubin – Hy's Law," for further instructions.

6.4.3. Recording of adverse events

6.4.3.1. Time period for collection of adverse events

Adverse events (including SAEs) will be collected from screening (Visit 1) throughout the treatment period (Visits 2 through 20) and including the follow-up period (Visit 21).

6.4.3.2. Follow-up of unresolved adverse events

Any AEs that are unresolved at the patient's last study visit are followed up by the investigator for as long as medically indicated, but without further recording in the eCRF. The sponsor or its designated safety representative retains the right to request additional information for any patient with ongoing AE(s)/SAE(s) at the end of the study, if judged necessary.

6.4.3.3. Intensity of adverse events

The following ratings will be used by the investigator to judge AE intensity:

- Mild: awareness of sign or symptom, but easily tolerated
- Moderate: discomfort sufficient to cause interference with normal activities
- Severe: incapacitating, with inability to perform normal activities

It is important to distinguish between serious and severe AEs. Severity is a measure of intensity whereas seriousness is defined by the criteria in Section 6.4.2. An AE of severe intensity need not necessarily be considered serious. For example, nausea that persists for several hours may be considered severe nausea, but not a SAE. On the other hand, a stroke that results in only a limited degree of disability may be considered a mild stroke but would be an SAE.

6.4.3.4. Causality collection

The investigator will assess causal relationship of all AEs.

A guide to the interpretation of the causality question is found in Appendix B to the Clinical Study Protocol.

6.4.3.5. Adverse events based on signs and symptoms

All AEs spontaneously reported by the patient or study partner or reported in response to the open question from the study personnel: "Have you had any health problems since you were last asked?" or revealed by observation will be collected and recorded in the eCRF. When collecting AEs, the recording of diagnoses is preferred (when possible) to recording a list of signs and symptoms. However, if a diagnosis is known, and there are other signs or symptoms that are not generally part of the diagnosis, the diagnosis and each sign or symptom will be recorded separately.

6.4.3.6. Adverse events based on examinations and tests

The results from protocol-mandated laboratory tests, vital sign measurements, ECG results, and other safety assessments will be summarized in the clinical study report.

If deterioration in a laboratory value or vital sign is associated with clinical signs and symptoms, the sign or symptom will be reported as an AE and the associated laboratory result or vital sign will be considered as additional information. Wherever possible the reporting investigator uses the clinical, rather than the laboratory, term (eg, anemia versus low hemoglobin value). In the absence of clinical signs or symptoms, clinically relevant deteriorations in non-protocol-

mandated laboratory tests, vital sign measurements, ECG results, and other safety assessments should be reported as AE(s).

Any new or aggravated, clinically relevant abnormal medical finding at a physical examination as compared with the baseline assessment will be reported as an AE.

6.4.3.7. Vasogenic edema

If a patient develops symptoms believed to be suggestive of vasogenic edema, such as headache, confusion, gait disturbance, or visual disturbance, these should be recorded as AEs and an MRI should be obtained. Study treatment should be discontinued if clinically significant symptomatic vasogenic edema, clinically significant symptomatic superficial siderosis, or clinically significant symptomatic incident microhemorrhage is seen (see Section 5.9 for suspension of study treatment). Following the study treatment discontinuation, the MRI scan should be repeated within 4 weeks to evaluate the status of the finding and then performed every 4 to 6 weeks (or as clinically indicated) until the finding resolves or stabilizes. Treatment with high-dose dexamethasone is to be considered, should symptoms be severe.

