5.8. Discontinuation of study treatment

Patients must be discontinued from study treatment in the following situations:

- Patient decision. The patient is at any time free to discontinue treatment, without prejudice to further routine clinical care.
- Adverse event or clinically significant laboratory value, ECG result, or vital sign
 measurement of such severity that, in the opinion of the investigator or medical monitor,
 continued treatment is not in the best interest of the patient
- Severe non-compliance to the study protocol that results in a safety concern, in the judgment of the investigator
- The patient, for any reason, requires a treatment with an excluded therapeutic agent for which temporary suspension of study treatment cannot be achieved (see Section 5.9). In this case, discontinuation from study drug occurs prior to introduction of the new agent.
- The patient develops a significant uncontrolled medical condition, such as a
 neuropsychiatric disorder that meets one of the exclusion criteria that in the opinion of
 the investigator after appropriate medical assessment, would pose an unacceptable risk to
 the patient if they were to continue receiving study drug.

Patients may be discontinued from study treatment in the following situations:

- An individual patient enrolled in the study may be discontinued from dosing based on a specific AE profile, as recommended by the IDMC, the CC medical monitor, and/or the sponsor Global Study Physician/Scientist, in discussions with the Principal Investigator.
- Incorrect enrollment (Section 5.3)
- Vasogenic edema (Section 6.4.3.7)
- Elevated liver enzymes (Section 6.4.5.1)

The study may be paused or stopped by either the IDMC or the sponsor at any time.

Procedures for discontinuation

A patient who decides to discontinue study treatment will always be asked about the reason(s) and the presence of any AEs. Any reported AEs will be followed up (See Sections 6.4.3 and 6.4.4).

All study medication should be returned to the investigational site.

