5.9. Suspension of study treatment

Treatment suspension and re-dosing of study drug can be considered based on the Principal Investigator's judgment, if clinical symptoms have resolved or a short-course of a prohibited medication is required. The maximum cumulative permissible treatment suspension is 6 weeks. Please contact your sponsor-designated medical monitor or designee for assistance.

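### The stop for symptomatic vasogenic edema, superficial siderosis or microhemorrhage points to a suspension rule whose restart condition ignores the MRI finding

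*Protocol*

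**What the plan says.** Protocol Section 6.4.3.7 (Vasogenic edema) covers patients with suggestive symptoms such as headache or confusion: "these should be recorded as AEs and an MRI should be obtained". It then gives a stopping rule with three triggers, the first two being vasogenic edema and superficial siderosis, each when symptomatic and clinically significant; for these, drug should be stopped. The third trigger carries the pointer to the suspension rule: "clinically significant symptomatic incident microhemorrhage is seen (see Section 5.9 for suspension of study treatment"). The next step is imaging: "Following the study treatment discontinuation, the MRI scan should be repeated within 4 weeks to evaluate the status of the finding". Further scans follow every 4 to 6 weeks, or as clinically indicated, until the finding has resolved or is stable.

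Section 5.9 (Suspension of study treatment) is a general rule. On the Principal Investigator's judgment, suspension and re-dosing can be considered "if clinical symptoms have resolved or a short-course of a prohibited medication is required". It adds: "The maximum cumulative permissible treatment suspension is 6 weeks". Sites are asked to contact the medical monitor for assistance; approval is not required. MRI is not mentioned.

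Section 5.8 (Discontinuation of study treatment) has two lists. The mandatory list includes an adverse event so severe that, in the opinion of the investigator or the medical monitor, continuing is not in the patient's best interest. The permissive list opens "Patients may be discontinued from study treatment in the following situations" and contains the entry "Vasogenic edema (Section 6.4.3.7").

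**The concern.** The stop and the restart rest on different evidence. Treatment stops because symptoms are present **and** a lesion is seen on MRI. The rule to which the sentence points lets a restart be considered when the symptoms alone have gone. No dosing decision depends on the repeat MRI, although its stated purpose is to check the finding.

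Sites could therefore treat the same patient differently. One keeps the patient off drug. Another restarts once the headache or confusion clears, before a scan has shown whether the edema or bleeding has resolved. Section 6.4.3.7 also suggests high-dose dexamethasone for severe symptoms. It is my inference, not a statement in the protocol, that symptoms could settle under such treatment while the lesion remains.

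The choice of word has practical consequences. Under Sections 5.8 and 5.10, a patient whose treatment is discontinued has early-discontinuation assessments, has no further PK or PET assessments and cannot enter the extension study. A patient who is suspended and re-dosed can stay on treatment.

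**Working it through.** No statistical figure is involved, so the check sets the provisions side by side and tests the timing.

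**1. Trigger against restart condition**

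| Step | Source | Symptoms | MRI finding |
|---|---|---|---|
| Stop | Section 6.4.3.7 | Required (clinically significant, symptomatic) | Required (lesion seen) |
| Follow-up scan | Section 6.4.3.7 | Not a condition | Assessed within 4 weeks, then every 4 to 6 weeks until resolved or stable |
| Restart may be considered | Section 5.9 | Resolved, on investigator judgment | Not mentioned |

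Section 5.9 also allows suspension for a short course of a prohibited medication. That route is not relevant here. For this event the test is investigator judgment plus resolved symptoms.

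**2. Window without a repeat image**

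The first repeat MRI is due by week 4 after the stop. If symptoms clear at week t, with t below 4, and the scan is done at the week-4 limit, re-dosing may be considered for 4 − t weeks with no repeat image. The upper bound, as t approaches 0, is 4 weeks. After week 4 a result should exist, but nothing makes the restart depend on it.

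**3. Can the scan come before a restart under the 6-week limit?**

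- With no earlier suspension, a scan at week 4 leaves 6 − 4 = 2 weeks of the cumulative limit.
- With s weeks already used, 6 − s weeks remain. A week-4 scan still fits if 6 − s ≥ 4, that is s ≤ 2.
- For s = 3 or s = 4, the scan would be needed by week 3 or week 2. A scan that early is allowed, because the requirement is *within* 4 weeks.
- After a week-4 scan, the next scheduled scan falls at week 4 + 4 = 8 to 4 + 6 = 10, beyond the limit. A lesion still evolving at week 4 would therefore normally mean that the patient stays off drug, which is what Section 6.4.3.7 already prescribes.

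So an imaging condition fits inside the present schedule and the present limit.

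**4. What already stands in the way of an early restart**

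- Section 5.9: investigator judgment is part of the test, and the medical monitor is to be contacted.
- Section 5.8: the mandatory adverse-event stop reaches these cases, because the symptoms are recorded as adverse events. It rests on opinion, not on an imaging criterion.
- Section 6.4.9.3: MRI findings of potential clinical significance are reported to the investigator and the sponsor. This reporting does not govern restart.

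**The case against.** The strongest reply is that this is clinical judgment, reasonably delegated. Section 5.9 is a general rule in which an imaging criterion would not be expected, and the event-specific section already supplies the imaging. A premature restart would need an investigator who had just seen symptomatic edema or bleeding on MRI to ignore the repeat scan, with no objection from the medical monitor. Either of them alone can invoke the mandatory stop, and the IDMC reviews safety data quarterly. Amyloid-related imaging abnormalities are not named among the potential risks in Section 1.5.2 or the topics of specific interest in Section 6.4.10. Both lists are non-exhaustive, and Section 6.4.9.3 does use MRI to monitor for these abnormalities.

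Most of this stands, and it is why the point is minor. It does not remove the gap: the one sentence that tells sites to stop sends them to a restart rule that does not mention the lesion.

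A reader might infer three stronger things that the protocol does not support:

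- *That Section 5.8 contradicts Section 6.4.3.7.* The permissive entry names vasogenic edema without qualification, so it also covers asymptomatic and non-significant cases. A stricter rule for the clinically significant symptomatic subset is compatible with that wider permission.
- *That the 6-week limit conflicts with the MRI schedule.* It does not: the first repeat scan can fall inside it, and a lesion that outlasts it leaves the patient off drug.
- *That the protocol tells sites to re-dose.* It only lets re-dosing be considered.

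**Conclusion.** The point holds as a minor safety-wording defect, worth correcting as a cheap improvement. Section 6.4.3.7 sets discontinuation as the response, yet links it to a restart rule looser than its trigger. Re-dosing may be considered while the lesion persists, or for up to 4 weeks before the repeat scan.

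The 4-week figure is the length of the unguarded interval and does not measure risk. It assumes that symptoms clear early and that the scan is done at the end of its permitted window. The protocol gives no rate for these events, so no number of affected patients is claimed. Endpoint, analysis sets, sample size, power and error control are untouched. A statistical analysis plan would not settle the matter, because it is a dosing instruction that sites follow from the protocol.

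**What to change.** In Section 6.4.3.7, keep discontinuation as the default and replace the parenthetical pointer to Section 5.9 with this sentence:

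> Re-dosing under Section 5.9 may be considered only in consultation with the medical monitor, when symptoms have resolved and the repeat MRI required below shows that the finding has resolved or stabilized, within the cumulative 6-week limit; otherwise treatment stays discontinued.

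Resolution or stabilization is already the end point of the MRI follow-up in that section, so no new imaging criterion is introduced. Sections 5.8 and 5.9 and the scan schedule stay as they are.

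The cost is one replaced parenthesis in the next amendment, with no extra scan, visit or patient. The downside is that some patients restart later, because they wait for a scan that may not be done until 4 weeks after the stop. Others do not restart at all, because the finding has neither resolved nor stabilized within the limit.

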6.4.3.8. Rash

In the event a patient experiences a suspected drug-induced rash, the following procedures should be followed:

- The patient should be referred to a dermatologist for an expert opinion.
- A photograph of the rash should be taken.
- A blood sample should be drawn for PK analysis.
- A punch biopsy may be obtained at the discretion of the dermatologist.

If treatment is discontinued due to a suspected drug-induced rash, the CC medical monitor should be notified as soon as possible, even if the rash did not meet the definition of an SAE.

6.4.3.9. Depression

In the event a patient experiences a clinically significant worsening of depression or a new onset major depression, the following procedures should be followed:

- The investigator or another qualified study physician should assess the patient clinically as soon as it is possible, and any appropriate emergency measures should be undertaken.
- Assuming an evaluation by a psychiatric emergency service is not required, the patient should be referred to a psychiatrist for an expert opinion.
- The investigator may initiate psychiatric management, including the use of psychiatric medication, as clinically needed.

 If study treatment is discontinued due to depression, the CC medical monitor should be notified as soon as possible, even if the event did not meet the definition of an SAE.

6.4.3.10. Disease progression

Disease progression can be considered as a worsening of a patient's condition attributable to the disease for which the investigational product is being studied. It may be an increase in the severity of the disease under study and/or increases in the symptoms of the disease. Gradual deterioration of cognition and/or function consistent with the usual course of AD should be considered as disease progression and not an AE. Events that are unequivocally due to disease progression should not be reported as AEs during the study.

6.4.4. Reporting of serious adverse events

All SAEs must be reported, whether or not considered causally related to the study medication or to the study procedure(s). All SAEs will be recorded in the source documents and in the eCRF.

If any SAE occurs in the course of the study, then the investigator or other site personnel will inform the designated sponsor or representative within 1 day of when he or she becomes aware of it, ie, immediately, but no later than 24 hours from the time he or she becomes aware of it, using the SAE Report Form. Telephone reports must be confirmed promptly by submitting the completed SAE Report Form by facsimile.

For fatal or life-threatening AEs where important or relevant information is missing, active follow-up will be undertaken immediately. The investigator or other site personnel will inform sponsor or representatives of any follow-up information on a previously reported SAE within 1 calendar day of when he or she becomes aware of it, ie, immediately, but no later than 24 hours from the time he or she becomes aware of it.

6.4.5. Laboratory safety assessment

Blood and urine samples for determination of hematology and clinical chemistry parameters, electrolytes, thyroid-stimulating hormone, total thyroxine, and urinalysis will be taken at the times indicated in the Study Plan (see Table 2). The date of collection of all laboratory tests will be recorded in the eCRF.

At screening, the clinical chemistry tests will include a lipid panel and creatinine clearance. At this visit, all patients will be tested for HbA1c, vitamin B12 level, folic acid, rapid plasma reagin (RPR), hepatitis B surface antigen, antibodies to hepatitis C, prothrombin time, partial thromboplastin time, and international normalized ratio (INR). Urine will be tested for drugs of abuse at screening. Human immunodeficiency virus may be tested at the discretion of the investigator or if mandated by local regulatory authority. This test may require a separate informed consent.

A follicle-stimulating hormone test will be performed at screening for female patients who report 6 to 12 months of spontaneous amenorrhea. The results of this test will be used to determine if the patient meets criteria for exclusion from the study.

The laboratory variables to be measured are listed in Table 5.

Table 5.Safety Laboratory Variables

Variables in serum/blood and urine				
Hematology (blood)	Electrolytes (serum)			
Hematocrit	Bicarbonate			
Hemoglobin	Chloride			
Leukocyte (white blood cell count, WBC) count	Phosphate			
Absolute leukocyte differential count (neutrophils,	Potassium			
basophils, monocytes, eosinophils and lymphocytes)	Sodium			
Platelet count				
Coagulation	Urinalysis			
Prothrombin timea	Blood			
Partial thromboplastin time ^a	Color			
International normalized ratio (INR)a	Glucose			
	Ketones			
Clinical chemistry (serum)	Leukocyte esterase			
Alanine aminotransferase (ALT)	pН			
Albumin	Protein			
Alkaline phosphatase	Specific gravity			
Aspartate aminotransferase (AST)				
Bilirubin, total	Screening tests ^a			
Blood urea nitrogen (BUN)	Folic acid			
Cholesterol (total, HDL, LDL) and triglycerides ^a	Hepatitis B surface antigen			
Calcium, total	Hepatitis C antibodies			
C-reactive protein	RPR			
Creatine kinase (CK)	Vitamin B12			
Creatinine	Urine test for drugs of abuse			
Creatinine clearance ^a				
Glucose	Other			
	Hemoglobin A1c (HbA1c)c			
Endocrinology				
Follicle-stimulating hormone (FSH)a,b	Optional/Confirmatory Testing			
Thyroid-stimulating hormonec	Human immunodeficiency virusa			
Total thyroxine ^c	Hepatitis C PCR ^d			

^a At screening only.

Abbreviations: HDL High-density lipoproteins; LDL Low-density lipoproteins; PCR polymerase chain reaction; RPR Rapid Plasma Reagin.

Laboratory values outside the reference limit suspected to be of any clinical significance will be repeated. Patients for whom suspected clinical significance is confirmed will either not be enrolled or, if already enrolled, will be followed until normalization or for as long as the

Only for female patients for whom the investigator believes menopausal status is uncertain who report between and 12 months of spontaneous amenorrhea

^c At screening, Week 52, and Week 104 (or final study visit) only.

d Patients with positive HCV antibodies may have a follow-up PCR test ordered.

Investigator considers necessary. Additional laboratory tests may be performed for safety reasons if judged appropriate by the investigator. See Section 6.4.3 for information regarding the recording of AEs based on laboratory tests. All laboratory samples will be analyzed using routine methods per the central laboratory, as referenced in the Laboratory Manual for this study.

For blood volume, see Section 7.1.

